#### 6.3. Trial Design

The following sections describe information and procedures involving study subjects. Additional, detailed information will be explained in the study's Manual of Procedures (MOP).

# 6.4. Study Endpoints

#### 6.4.1. Primary Endpoints

The primary endpoints to assess safety are TEAEs; SAEs; Suspected, Unexpected, Serious Adverse Reactions (SUSARs); and death.

#### 6.4.2. Secondary Endpoints

The following secondary endpoints will only be evaluated in Cohort 3 subjects:

• Change in pre- and post-infusion values for Prothrombin Time and International Normalized Ratio (PT/INR), aPTT, Factors I, II, V, VII, VIII, IX, X, XI, D-DIMER, von Willebrand Factor activity, Protein S activity, Protein C activity, Prothrombin

Fragments 1+2 (PF 1+2), Thrombin/Antithrombin (TAT), Antithrombin III (AT-III), Alpha-2 antiplasmin, and C3a des Arg activity compared to pre-infusion values after infusion of 3 units of FDP compared to 3 units of FFP; and

• Determine if the changes in specific hematology, urinalysis, vital signs, DAT, and chemistry values are similar within clinically meaningful levels after infusion of either 3 units of autologous FDP or FFP.

# 6.5. Overall Study Design

This single-site, partial double-blind study in healthy volunteers is designed to assess the safety of infusing ascending doses of reconstituted autologous FDP in 3 fixed-dose cohorts. Subjects in Cohort 1 will receive 1 unit of FDP, which is approximately 270 mL. Subjects in Cohort 2 will receive 2 FDP units, which total approximately 540 mL. Cohorts 1 and 2 are the lower-dose cohorts. Subjects will be assigned to these beginning with the lowest dose, Cohort 1. In the absence of TEAEs, SAEs or the implementation of protocol stopping rules (SRs), and with Data and Safety Monitoring Board (DSMB) recommendation and Sponsor approval subjects assigned to Cohort 2 will be infused with an increased dose of 2 units. For both of these cohorts subjects will also be assigned to 1 of 2 single infusion treatment arms:

- 1. Infusion of FDP manufactured with autologous plasma derived from WB (FDP-CPD), at the corresponding dose; or
- 2. Infusion of FDP manufactured with autologous plasma collected by plasmapheresis (FDP-ACD), at the corresponding dose.

In the absence of TEAEs, SAEs, or the implementation of protocol stopping rules (SRs) in Cohort 2 subjects, infusions in Cohort 3 subjects may be implemented. Cohort 3 is designed as a randomized, controlled, crossover infusion of 3 units of FDP (approximately 810 mL) and 3 units of FFP (approximately 810 mL) at separate visits. Subjects are randomized to a specific infusion schedule of either 3 units of FDP or 3 units of FFP at the first infusion visit, followed by infusion with the alternate product at the second infusion visit. Crossover of FDP and FFP enables comparison of infusion safety and select coagulation factor recoveries within the same subjects between FDP and FFP at this higher dose. Unlike Cohorts 1 and 2, the FDP and FFP infusion products in Cohort 3 are sourced solely from autologous plasmapheresis donations (FDP-ACD). A 2-week period between infusion visits is required for all Cohort 3 subjects regardless of infusion schedule.

Use of autologous plasma in the trial assists in the elimination of potential AEs related to allogeneic plasma infusion, but it also adds additional burden to participating subjects who, upon consent and enrollment, need to donate sufficient volume of plasma to provide the autologous plasma needed for the trial infusions (eg, manufacture of autologous FDP units in all cohorts; in Cohort 3, the additional need for FFP in addition to FDP). Blood donation standards typically require a 56-day interval between WB donations; however, a shortened study donation period of a minimum of 28 days between WB donations will be used for study subjects. Without the loss of RBCs in plasmapheresis, these types of donations can be made more frequently, with a minimum of 7 days between donations. Plasmapheresis donations yield up to 800 mL plasma depending on donor size. Thus, the trial's overall design and use of plasmapheresis alone in Cohort 3 reduces the frequency in which subjects will need to donate due to significantly larger estimated plasma volumes per donation. Plasmapheresis offers practical advantages and using

FDA's guidance regarding automated plasma collection volumes, reduces potential safety implications (FDA-1992).

Subjects in Cohorts 1 and 2 will provide sufficient plasma volume for a single infusion with either 1 or 2 units, respectively. Based on assigned treatment arm, subjects will provide plasma through either WB or plasmapheresis collection for manufacture of autologous FDP-CPD or FDP-ACD. Cohort 2 subjects in the FDP-CPD treatment arm are required to successfully make 2 WB donations within a relatively short period of time to provide adequate volume for their use in the trial. Because of the extraordinarily long time required to accrue sufficient WB-derived plasma for the high dose cohort (approximately 11 months), the FDP-CPD treatment arm is not included in Cohort 3. The total starting volume of plasma needed from each Cohort 3 subject is approximately 1620 mL; triple that of Cohort 2 and thus inclusion of this treatment arm in Cohort 3 would require 6 WB donations, increasing subject risk for significant iron store depletion and anemia. Table 3 provides details on assigned cohorts and treatment arms as well as indicates the type, frequency, and total volume of blood/plasma donations required.

**Table 3:** Cohort and Treatment Arm Details

Dose Cohorts and Treatment Arms	Number of Subjects	Donation Type	Approximate Volume Autologous Plasma Required	Number of Donations			
Cohort 1: One unit single infusion [approximately 270 mL]							
Arm 1: FDP-CPD	4	WB	270	1			
Arm 2: FDP-ACD	4	Plasmapheresis	270	1			
Cohort 2: Two units single infusion [approximately 540 mL]							
Arm 3: FDP-CPD	4	WB	540	2			
Arm 4: FDP-ACD	4	Plasmapheresis	apheresis 540				
Cohort 3: Three units crossover infusion [approximately 810 mL, each]							
Arm 5: FDP ACD x FFP	4	Plasmapheresis	1,620	3-41			
Arm 6: FFP x FDP ACD	4	Plasmapheresis	1,620	3-41			

The following SRs will be applied to all study subjects throughout the trial:

- 1. An SAE that is determined to be possibly, probably, or definitely related to the study product;
- 2. An AE related to the study product that the PI, RM, and/or sponsor's PVG MD agree jeopardizes the subject's health or safety;
- 3. An AE related to the study product that requires medical or surgical intervention to prevent occurrence of an SAE;
- 4. A post-infusion, abnormal coagulation function assay which is also a greater than 20% change from baseline for PT/INR and/or aPTT values (eg, a subject who has a baseline INR of 1.0 with a post-infusion INR of 1.3 will activate an SR, because this is an

- abnormal coagulation function assay result that is also a greater than 20% change from the pre-infusion assay result); and/or
- 5. Post-infusion development of hemolysis or deep vein thrombosis (DVT), cardiac ischemia, or pulmonary embolism (PE). DVT will be determined following the Institute for Clinical Systems Improvement (ICSI) Health Care Guideline: Venous Thromboembolism Diagnosis and Treatment (includes assessment of D-Dimer results and Wells criteria ≥ 2) (Dupras et al-2013).

If any of the above conditions occur, the study will be paused to assess continuation of the study.

The DSMB will convene after completion of each cohort. DSMB meetings will be scheduled to maximize the amount of subject data reported to the DSMB through the 28-day follow-up visit. The DSMB will have at a minimum all data through the 7-Day Follow-Up Visit. Following each meeting, the DSMB will provide the sponsor with a recommendation about proceeding with infusions in the subsequent cohort. Following the review of Cohort 3 data, the DSMB will provide a recommendation about proceeding with the next planned FDP trial. After the receipt and consideration of a DSMB recommendation, the sponsor will make a final determination about proceeding to the next cohort or the next FDP trial. It is up to the sponsor to make a final determination on how to proceed.

Table 4: Study Events Schedule for Cohort 1, Arms 1 and 2

Visit Activities:	Visit 1 Screening	Visit 2 WB/Plasmapheresis Collection	Visit 3 Infusion	Visit 4  24-Hour Follow-Up	Phone Calls L 48 & 72 hrs	Visit 5  7-Day Follow-Up	Phone Call L 14-Day	Visit 6  28-Day Follow-Up
Study Day*:	-56 to -49	-35	1	2	3 & 4	8	15	29
Visit Window:				± 3 hrs	± 2 hrs	± 1 day	± 2 hrs	± 1 day
General Procedures								
Informed Consent	X							
Inclusion/Exclusion Criteria	X							
Demographic Questionnaire	X							
AABB Donor History Questionnaire A	X	X						
Duke Activity Status Index	X							
Subject Medical Health Standardized Questionnaire B	X	X	X	X		X		X
Complete Physical Exam C	X		X	X				
Abbreviated Physical Exam D		X				X		X
Wells Scale H	X		X	X				
Vital Signs E	X	X	X H	X		X		X
Concomitant Medications	X	X	X	X	X	X	X	X
AEs		X	X	X	X	X	X	X
Blood/Plasma Collection F		X						
FDP Infusion			X					
Visual Inspection of Blood Components		X	X					
Exit Interview G								X
Laboratory Tests								
Urine Drug Screening	X							
Urine Pregnancy Test (females only)	X		X K					
Urinalysis	X		XK	X				
Chemistry Panel I	X		XK	X		X		
Complete Blood Count (CBC) J	X		XK	X		X		X
Hematocrit		X						
PT/INR, aPTT	X		XK	X				X

Table 4: Study Events Schedule for Cohort 1, Arms 1 and 2 (continued)

Visit Activities:	Visit 1	Visit 2	Visit 3	Visit 4	Phone Calls L	Visit 5	Phone Call L	Visit 6
	Screening	WB/Plasmaph eresis Collections	Infusion	24-Hour Follow- Up	48 & 72 hrs	7-Day Follow-Up	14-Day	28-Day Follow-Up
Study Day*:	-56 to -49	-35	1	2	3 & 4	8	15	29
Visit Window:				± 3 hrs	±2 hrs	± 1 day	± 2 hrs	± 1 day
Direct Antiglobulin Test (DAT) (Immunoglobulin G (IgG) and Complement Factor 3 (C3))	X		X K	X				X
D-Dimer Test	X		χĸ	X				
Blood Type for ABO and Rh	X		X K					
Red-Cell Antibody Screen	X							
Syphilis Screen	X							
HTLV Antibody Screening Test	X							
HIV-1/2, HBV, HCV, and West Nile Virus Nucleic Acid Tests	X							
Cross-match RBC vs FDP			X K					
Reverse Type of FDP			XK					
SPEP M		X						

\*The estimated manufacturing time is 5 weeks.

<sup>A The AABB donor history questionnaire is administered at all donation visits.

<sup>BConfirm data are accurate; subject is healthy with no significant medical history change.

<sup>C Complete physical exams to include height (screening only), weight, vital signsE, and a targeted assessment of health as described in section 7.2 and section 8.2.

<sup>D Abbreviated physical exam to include vital signsE and a general assessment of health.

E Vital signs monitored include blood pressure, heart rate, respiration rate, and temperature. These will be measured every 15 minutes (± 5 minutes) during the infusion, every 30 minutes (± 5 minutes) between 0 and 4 hours post-infusion, and then every 4 hours (±40 minutes) until the subject is released from the clinic.

<sup>FBlood and plasma collection will generally be done approximately 5 weeks before the study infusion in order to allow sufficient time for product preparation, testing, release, and shipment back to the site.

<sup>GExit interview may take place at any point during the study and is dependent upon subject's continued enrollment status.

<sup>H Monitor vital signs every 15 minutes during infusion; every 30 minutes for up to 4 hours post-infusion; and after 6 hours, vital signs should be measured every 4 hours until the subject is released. Subjects assessed for DVT, PE, and cardiac ischemia using the Wells Scale prior to infusion, at 30 minutes, 4 hours, and 24 hours post-infusion before the subject can be released from the clinic.

<sup>1Chemistry panel includes Calcium, Alkaline Phosphatase (ALP), Alanine Aminotransferase (ALT), Aspartate Aminotransferase (AST), Bicarbonate, Chloride, Glucose, Potassium, Sodium, Total Bilirubin, Total Protein, Blood Urea Nitrogen (BUN), Lactate, and Creatinine. The chemistry panel also includes pH, Ionized Calcium, and Total Magnesium, which will only be measured at pre-infusion and 0.5 hour post-infusion.

<sup>1CBC comprises Hematocrit, Hemoglobin, Platelet Count, RBC Count, and White Blood Cell (WBC) Count.

<sup>K See Table 7 – Laboratory Testing Schedule and Volumes for Cohorts 1 and 2 for laboratory testing details. L

Follow-up phone calls to the subject will be made 48 hours, 72 hours, and 14 days post infusion.

M SPEP performed for subjects undergoing plasmapheresis only.

Table 5: Study Events Schedule for Cohort 2, Arm 3

Visit Activities:	Visit 1	Visits 2a/2b	Visit 3	Visit 4	Phone Calls L	Visit 5	Phone Call L	Visit 6
	Screening	WB	Infusion	24-Hour	48 & 72 hrs	7-Day	14-Day	28-Day
		Collections		Follow-Up		Follow-Up		Follow-Up
Study Day*:	-84 to -77	-63 to -35	1	2	3 & 4	8	15	29
Visit Window:				± 3 hrs	± 2 hrs	± 1 day	± 2 hrs	± 1 day
General Procedures								
Informed Consent	X							
Inclusion/Exclusion Criteria	X							
Demographic Questionnaire	X							
AABB Donor History Questionnaire A	X	X						
Duke Activity Status Index	X							
Subject Medical Health Standardized Questionnaire B	X	X	X	X		X		X
Complete Physical Exam C	X		X	X				
Abbreviated Physical Exam D		X				X		X
Wells Scale H	X		X	X				
Vital Signs E	X	X	XH	X		X		X
Concomitant Medications	X	X	X	X	X	X	X	X
AEs		X	X	X	X	X	X	X
Blood Collection F		X						
SPEP F		X						
FDP Infusion			X					
Visual Inspection of Blood Components		X	X					
Exit Interview G								X
Laboratory Tests								
Urine Drug Screening	X							
Urine Pregnancy Test (females only)	X		XK					
Urinalysis	X		XK	X				
Chemistry Panel I	X		XK	X		X		
CBC 1	X		χĸ	X		X		X
Hematocrit		X	,					
PT/INR, aPTT	X		XK	X				X
DAT (IgG and C3)	X		XK	X				X
D-Dimer Test	X		XK	X				
Blood Type for ABO and Rh	X		XK					

Table 5:Study Events Schedule for Cohort 2, Arm 3 (continued)

Visit Activities:	Visit 1	Visits	Visit 3	Visit 4	Phone	Visit 5	Phone	Visit 6
		2a/2b			Calls L		Call L	
		WB		24-Hour		7-Day	14-Day	28-Day
	Screening	Collections	Infusion	Follow-Up	48 & 72 hrs	Follow-Up		Follow-Up
Study Day*:	-84 to -77	-63 to -35	1	2	3 & 4	8	15	29
Visit Window:				± 3 hrs	± 2 hrs	± 1 day	± 2 hrs	± 1 day
Red-Cell Antibody Screen	X							
Syphilis Screen	X							
HTLV Antibody Screening Test	X							
HIV-1/2, HBV, HCV, and West Nile	X							
Virus Nucleic Acid Tests								
Cross-match RBC vs FDP			XK					
Reverse Type of FDP			χĸ					

\*The estimated manufacturing time is 5 weeks.

<sup>AThe AABB donor history questionnaire is administered at all donation visits.

<sup>BConfirm data are accurate; subject is healthy with no significant medical history change.

<sup>CComplete physical exams to include height (screening only), weight, vital signsE, and a targeted assessment of health as described in section 7.2 and section 8.2

<sup>DAbbreviated physical exam to include vital signsE and a general assessment of health.

EVital signs monitored include blood pressure, heart rate, respiration rate, and temperature. These will be measured every 15 minutes (± 5 minutes) during the infusion, every 30 minutes (± 5 minutes) between 0 and 4 hours post-infusion, and then every 4 hours (± 40 minutes) until the subject is released from the clinic.

FBlood and plasma collections will generally be done approximately 5 weeks before the study infusion in order to allow sufficient time for product preparation, testing, release, and shipment back to the clinical site. Arm 3 requires 2 WB donations. SPEP only performed for subjects undergoing plasmapheresis.

<sup>GExit interview may take place at any point during the study and is dependent upon subject's continued enrollment status.

<sup>HMonitor vital signs every 15 minutes during infusion; every 30 minutes for up to 4 hours post-infusion; and after 6 hours, vital signs should be measured every 4 hours until the subject is released. Subjects assessed for DVT, PE, and cardiac ischemia using the Wells Scale prior to infusion, at 30 minutes, 4 hours, and 24 hours post-infusion before the subject can be released from the clinic.

<sup>1Chemistry panel includes Calcium, ALP, ALT, AST, Bicarbonate, Chloride, Glucose, Potassium, Sodium, Total Bilirubin, Total Protein, BUN, Lactate, and Creatinine. pH, Ionized Calcium and Total Magnesium will only be measured at pre-infusion and 0.5 hour post-infusion.

<sup>JCBC comprises Hematocrit, Hemoglobin, Platelet Count, RBC Count, and WBC Count.

<sup>KSee Table 7 - Laboratory Testing Schedule and Volumes for Cohorts 1 and 2 for laboratory testing details.

<sup>L Follow-up phone calls to the subject will be made 48 hours, 72 hours, and 14 days post infusion.

Table 6: Study Events Schedule for Cohort 2, Arm 4

Visit Activities:	Visit 1	Visit 2	Visit 3	Visit 4	Phone Calls L	Visit 5	Phone Call L	Visit 6
	Screening	Plasmapheresis Collection	Infusion	24-Hour Follow-Up	48 & 72 hrs	7-Day Follow-Up	14-Day	28-Day Follow-Up
Study Day*:	-56 to -49	-45 to -35	1	2	3 & 4	8	15	29
Visit Window:				± 3 hrs	±2 hrs	± 1 day	±2 hrs	± 1 day
General Procedures								
Informed Consent	X							
Inclusion/Exclusion Criteria	X							
Demographic Questionnaire	X							
AABB Donor History Questionnaire A	X	X						
Duke Activity Status Index	X							
Subject Medical Health Standardized Questionnaire B	X	X	X	X		X		X
Complete Physical Exam C	X		X	X				
Abbreviated Physical Exam D		X				X		X
Wells Scale H	X		X	X				
Vital Signs E	X	X	XH	X		X		X
Concomitant Medications	X	X	X	X	X	X	X	X
AEs		X	X	X	X	X	X	X
Plasma Collection F		X						
FDP Infusion			X					
Visual Inspection of Blood Components		X	X					
Exit Interview G								X
Laboratory Tests								
Urine Drug Screening	X							
Urine Pregnancy Test (females only)	X		χĸ					
Urinalysis	X		XK	X				
Chemistry Panel I	X		XK	X		X		
CBC 1	X		XK	X		X		X
Hematocrit		X	1					
PT/INR, aPTT	X		XΚ	X				X
DAT (IgG and C3)	X		XK	X				X
D-Dimer Test	X		XK	X				
Blood Type for ABO and Rh	X		XK					

Table 6: Study Events Schedule for Cohort 2, Arm 4 (continued)

Visit Activities:	Visit 1	Visit 2	Visit 3	Visit 4	Phone Calls L	Visit 5	Phone Call L	Visit 6
	Screening	Plasmapheresis Collection	Infusion	24-Hour Follow-Up	48 & 72 hours	7-Day Follow-Up	14-Day	28-Day Follow-Up
Study Day*:	-56 to -49	-45 to -35	1	2	3 & 4	8	15	29
Visit Window:				± 3 hrs	± 2 hrs	± 1 day	± 2 hrs	± 1 day
Red-Cell Antibody Screen	X							
Syphilis Screen	X							
Screening Test for HTLV Antibody	X							
Nucleic Acid Tests for HIV-1/2,	X							
HBV, HCV, and West Nile Virus								
Cross-match RBC vs. FDP/FFP			XK					
Reverse Type of FDP/FFP			XK					
SPEP M		X						

\*The estimated manufacturing time is 5 weeks.

<sup>AThe AABB donor history questionnaire is administered at all donation visits.

<sup>BConfirm data are accurate; subject is healthy with no significant medical history change.

<sup>C Complete physical exams to include height (screening only), weight, vital signsE, and a targeted assessment of health as described in section 7.2 and section 8.2.

<sup>DAbbreviated physical exam to include vital signsE and a general assessment of health.

EVital signs monitored include blood pressure, heart rate, respiration rate, and temperature. These will be measured every 15 minutes (± 5 minutes) during the infusion, every 30 minutes (± 5 minutes) between 0 and 4 hours post-infusion, and then every 4 hours (± 40 minutes) until the subject is released from the clinic.

FBlood and plasma collections will generally be done approximately 5 weeks before the study infusion in order to allow sufficient time for product preparation, testing, release, and shipment back to the clinical site. Cohort 2, Arm 4 subjects are expected to undergo 1 plasmapheresis procedure.

<sup>GExit interview may take place at any point during the study and is dependent upon subject's continued enrollment status.

<sup>HMonitor vital signs every 15 minutes during infusion; every 30 minutes for up to 4 hours post-infusion; and after 6 hours, vital signs should be measured every 4 hours until the subject is released. Subjects assessed for DVT, PE, and cardiac ischemia using the Wells Scale prior to infusion, at 30 minutes, 4 hours, and 24 hours post-infusion before the subject can be released from the clinic.

<sup>1Chemistry panel includes Calcium, ALP, ALT, AST, Bicarbonate, Chloride, Glucose, Potassium, Sodium, Total Bilirubin, Total Protein, BUN, Lactate, and Creatinine. pH, Ionized Calcium and Total Magnesium will only be measured at pre-infusion and 0.5 hour post-infusion.

<sup>JCBC comprises Hematocrit, Hemoglobin, Platelet Count, RBC Count, and WBC Count.

<sup>KSee Table 7 - Laboratory Testing Schedule and Volumes for Cohorts 1 and 2 for laboratory testing details.

<sup>L Follow-up phone calls to the subject will be made 48 hours, 72 hours, and 14 days post infusion.

<sup>M SPEP performed for subjects undergoing plasmapheresis. Total Protein will be performed STAT or up to 24 hours prior to plasmapheresis if a subject requires multiple collections.

Table 7: Laboratory Testing Schedule and Volumes for Cohorts 1 and 2

Laboratory Testing	Screening	Donation	Infusion Visi	t – Cohorts 1	and 2	24-Hour	Day 7	Day 28
, o		Visits	Pre-Infusion	Post-Ir	fusion	Follow-Up	Follow-Up	Follow-Up
				0.5 hr	4 hrs			
Urine Pregnancy Test (females only)	X		X					
Urine Drug Screening	X							
Urinalysis	X		X	X	X	X		
Chemistry Panel A	X		X	X	X	X	X	
CBC B	X		X	X	X	X	X	X
Hematocrit		X						
PT/INR	X		X	X	X	X		X
aPTT	X		X	X	X	X		X
DAT (IgG and C3)	X		X			X		X
D-Dimer	X		X	XE	XE	X		
Blood Type for ABO and Rh	X		Xc					
Red-Cell Antibody Screen	X							
Syphilis Screen	X							
Screening Test for HTLV Antibody	X							
Nucleic Acid Tests for HIV-1/2,	X							
HBV, HCV, and West Nile Virus								
Cross-match RBC			X					
Reverse Type FDP			X					
WB/Plasma Collection		X						
SPEP		XF						
Total Blood Volume Collected	~51mL	500 mL- 607 mL D	~36mL	~36mL	~30 mL	~34mL	~21mL	~20 mL

<sup>AChemistry panel includes Calcium, ALP, ALT, AST, Bicarbonate, Chloride, Glucose, Potassium, Sodium, Total Bilirubin, Total Protein, BUN, Lactate, and Creatinine. pH, Ionized Calcium and Total Magnesium will only be measured at pre-infusion and 0.5 hour post-infusion.

<sup>BCBC comprises Hematocrit, Hemoglobin, Platelet Count, RBC Count, and WBC Count.

<sup>CABO only at the pre-infusion sampling time.

<sup>DCollection volume range for this visit includes the WB (approximately 500 mL) or plasma donation volume (approximately 600 mL) collected at each visit. ED-Dimer collection at 30 minutes and 4 hours post-infusion must be done STAT. Results must be received and reviewed by the PI prior to the subject's release from the clinic.

FSPEP is performed for Cohort 2, Arm 4 subjects at each plasmapheresis session. Total Protein will be performed STAT or up to 24 hours prior to plasmapheresis if a subject requires multiple collections.

**Table 8:** Study Events Schedule for Cohort 3

Visit Activities:	Visit 1	Visits 2a-2d P	Visit 3	Visit 4	Phone Calls N	Visit 5	Visit 6	Visit 7	Phone Calls N	Visit 8	Phone Call N	Visit 9
	Screening	Plasmapheresis Collections	Infusion #1	24-Hour Follow- Up	48 & 72 hrs	7-Day Follow- Up	Infusion #2	24- Hour Follow- Up	48 & 72 hrs	7-Day Follow- Up	14-Day	28-Day Follow- Up
Study Day*:	-56 to -49	-55 to -35	1	2	3 & 4	8	15	16	17 & 18	22	29	43
Visit Window:				±3 hrs	± 2 hrs	± 1 day	± 3 days	± 3 hrs	±2 hrs	± 1 day	±2 hrs	± 1 day
General Procedures												
Informed Consent	X											
Inclusion/Exclusio n Criteria	X											
Demographic Questionnaire	X											
AABB Donor History Questionnaire A	X	X										
Duke Activity Status Index	X											
Subject Medical Health Standardized Questionnaire B	X	X	X	X		X	X	X		X		X
Complete Physical Exam C	X		X	X								
Randomization			X									
Abbreviated Physical Exam D		X				X	X	X		X		X
Wells Scale H	X		X	X			X	X				
Vital Signs E	X	X	X H	X		X	$X^{H}$	X		X		X
Concomitant Medications	X	X	X	X	X	X	X	X	X	X	X	X
AEs		X	X	X	X	X	X	X	X	X	X	X
Plasma Collection F		X	_		_						_	

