## 6.8. Duration of Subject Participation

Subjects in Cohort 1 will complete the study in approximately 3 months. Subjects in Cohort 2, Arm 3 will complete the study in approximately 4 months; subjects in Cohort 2, Arm 4 will require approximately 3 months. Subjects in Cohort 3 will complete the study in approximately 4 months. The first infusion for all cohorts is defined as Study Day 1. Study Day 15 is the second infusion for Cohort 3. The manufacturing time is currently estimated to be 5 weeks and although accounted for in study participation time, no subject activities are planned during this time. Screening and baseline assessment and informed consent visits will require approximately 2 hours. Final eligibility assessments and WB collection or plasmapheresis will require approximately 4 hours. On the day of infusion, the infusion and post-infusion studies will require approximately 8 hours.

For all cohorts, the on-site follow-up assessments will take 1 to 2 hours to complete, and the telephone assessments will take 15 to 20 minutes to complete. Cohorts 1 and 2 will have on-site follow-up assessments on Study Days 2, 8, and 29 and telephone follow-up assessments on Study Days 3, 4, and 15. Cohort 3 will have on-site follow-up assessments on Study Days 2, 8, 16, 22, and 43 and telephone follow-up assessments on Study Days 3, 4, 17, 18, and 29.

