### 7. SELECTION AND WITHDRAWAL OF SUBJECTS

## 7.1. Recruitment of Subjects

HBC maintains lists of potential study subjects who have previously donated WB or plasma at the site and have indicated an interest in participating in research studies. Site personnel will contact (Appendix D) those people who have indicated an interest in research participation to inform them about this study. If the potential subject expresses an interest in learning more about the study and/or participating, then a screening visit will be scheduled. In addition to this process, advertisements (Appendix E) for healthy volunteers may also be used to recruit subjects. The subjects are typically not socioeconomically disadvantaged.

Subjects will be screened for inclusion as they present to the clinical site with an interest in participating and provide written informed consent. Subjects will be selected based on inclusion/exclusion criteria and eligibility requirements as specified in the study protocol, without any limitations to gender or ethnicity.

Recruitment of Cohort 2 subjects will begin following the infusion of the last subject in Cohort 1. Enrollment, screening, and collection visits will be completed but infusion visits will not occur until the DSMB recommends and the Sponsor provides their approval to proceed. The same process will also be applied to the recruitment for Cohort 3 subjects. Concurrent infusions will

not take place across cohorts ensuring infusions at the next higher does do not begin until all subject infusions at the previous dose have been completed.

Refer to section 5.9 for a detailed description of the subject population.

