### 8.3.4. 28-Day Follow-Up Visit

A post-infusion follow-up visit will be scheduled 28 days ( $\pm$  1 day) post-infusion for subjects enrolled in Cohorts 1 and 2. For subjects enrolled in Cohort 3, a 28-day post-infusion follow-up visit will take place after the second plasma infusion, only, approximately 42 days after the first infusion visit. The following procedures will be performed at these follow-up visits:

- Review of medical history, concomitant medications, and AEs since the 14-day telephone follow-up contact;
- Abbreviated physical exam which includes vital signs (blood pressure, heart rate, respiration rate, and temperature) and a general assessment of health;
- Collect blood samples as noted for all tests listed in the Schedule of Events tables (Table 4, Table 5, Table 6, and Table 8); and
- Exit interview concluding the subject's study participation.

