A Data and Safety Monitoring Board (DSMB) will formally review study safety reports at the completion of each cohort. Cohort safety data reported to the DSMB will minimally include complete subject data through the 7-day post-infusion follow-up visit. Following each meeting, the DSMB will provide the sponsor with a recommendation about proceeding with infusions in the subsequent cohort or, at the conclusion of Cohort 3, about proceeding with the next planned FDP trial. After reviewing and considering the recommendation, the sponsor is responsible for making the final determination about whether to proceed.

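### The binding minimum for each DSMB escalation review is 7-day data, although on the planned schedule the last 28-day visit falls 20 to 27 days before the next dose could be given

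*Protocol*

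**What the plan says.** Protocol 6.5 states an aim and then a requirement. The aim is "DSMB meetings will be scheduled to maximize the amount of subject data reported to the DSMB through the 28-day follow-up visit". The requirement is "The DSMB will have at a minimum all data through the 7-Day Follow-Up Visit". The synopsis carries the same pair. SAP 1.1 keeps only the requirement: "Cohort safety data reported to the DSMB will minimally include complete subject data through the 7-day post-infusion follow-up visit".

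The board meets after each cohort is complete. Protocol 7.6.3 counts a Cohort 1 or 2 subject as complete once infused and seen at the 7-day visit, so a meeting held at that point complies.

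Protocol 6.5 makes escalation depend on there being no TEAEs, SAEs or triggered stopping rules, as well as on the board's recommendation and the sponsor's approval. Protocol 6.1 defines TEAEs as running from the start of infusion through the whole post-infusion follow-up.

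On timing, Protocol 7.1 says "Recruitment of Cohort 2 subjects will begin following the infusion of the last subject in Cohort 1", and for the next step "The same process will also be applied to the recruitment for Cohort 3 subjects". Next-cohort subjects may be screened and may donate, but are not infused until the board has recommended and the sponsor has approved. Protocol 6.8 adds: "The manufacturing time is currently estimated to be 5 weeks".

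**The concern.** The escalation condition covers the full follow-up, but the data the board must hold cover only its first week. For the most recently infused subjects, a board meeting at the minimum has no PT/INR, aPTT or DAT result after 24 hours and no AE information from Day 9 to Day 29, including the 14-day call. It would be recommending a higher dose of a product that Protocol 5.3 calls first-in-human without being able to confirm the condition it is asked to apply.

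A short floor is usually accepted because waiting would hold up the next cohort. Here next-cohort subjects must still be recruited, screened and bled, and their product manufactured, after the last lower-dose infusion, so most or all of the wait is already built into the plan.

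**Working it through.** **1. The plan's own durations.** The synopsis components, in weeks (screening + collection + manufacture + follow-up), reproduce the stated totals:
- Cohort 1 and Cohort 2 Arm 4: 2 + 1 + 5 + 4 = 12
- Cohort 2 Arm 3: 2 + 5 + 5 + 4 = 16
- Cohort 3: 2 + 3 + 5 + 6 = 16

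**2. What is measured when, Cohorts 1 and 2 (Protocol Table 7).**

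| Test | To 24 h post-infusion | Day 7 | Day 28 |
|---|---|---|---|
| PT/INR, aPTT | 0.5 h, 4 h, 24 h | no | yes |
| DAT | 24 h | no | yes |
| D-dimer | 0.5 h, 4 h, 24 h | no | no |
| CBC | 0.5 h, 4 h, 24 h | yes | yes |
| Chemistry | 0.5 h, 4 h, 24 h | yes | no |

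For the last subject infused, the follow-up unseen at the minimum is 28 − 7 = 21 of 28 days. Of six scheduled post-infusion contacts, two remain: the 14-day call and the 28-day visit.

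**3. Calendar.** Let t = 0 be the last lower-dose infusion. Both visits have a window of ±1 day.
- Last 7-day visit: t ≤ 7 + 1 = 8.
- Last 28-day visit: t ≤ 28 + 1 = 29 (Protocol 8.3.4).
- Earliest next-cohort infusion, E: recruitment starts only after t = 0. Protocol Table 6 (Arm 4, the faster Cohort 2 arm) and Table 8 (Cohort 3) put screening at Day −56 to −49 and infusion at Day 1. With no Day 0, E = 49 to 56.
- Slack after the last 28-day visit: 49 − 29 = 20 to 56 − 29 = 27 days.
- Counting manufacture alone (35 days): 35 − 29 = 6 days.
- For Cohort 3, the synopsis components give 2 + 3 + 5 = 10 weeks, or 70 days, and a slack of 70 − 29 = 41 days. This differs from Table 8, but either figure exceeds 29 days.

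**4. Delay from requiring 28-day data.** Let T be the days from the last required visit to the sponsor's decision. The documents do not give T, so 0 to 42 days is assumed.

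Added delay = max(0, 29 + T − E) − max(0, 8 + T − E)

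| T (days) | E = 49 | E = 56 |
|---|---|---|
| 0 to 20 | 0 | 0 |
| 27 | 7 | 0 |
| 28 | 8 | 1 |
| 35 | 15 | 8 |
| 42 | 21 | 15 |

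The delay cannot exceed 29 − 8 = 21 days.

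**5. A late replacement.** If the last subject leaves before the 7-day visit, Protocol 7.6.3 calls for a replacement, possibly after next-cohort recruitment has begun. That subject would be infused at about t = 49 to 56 and reach the 28-day visit by t = 78 to 85, after next-cohort product could be ready. Protocol 7.1 already holds the higher dose until all lower-dose infusions are done, so the extra wait is again at most 21 days.

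**The case against.** The strongest reply is that the plan already tells the sponsor to schedule for 28-day data. If there is as much slack as shown above, following that instruction delivers them. This is fair, and it limits the point to turning an aim into a requirement. But the aim binds no one, the SAP omits it, and a meeting at Day 8 would be fully compliant.

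A reader might infer more: that late coagulation and DAT results would be missed, that 28-day data always arrive first, and that the 7-day floor saves no time. The documents do not support these.
- **Missed.** The stopping rules apply to every subject throughout the trial, whatever the board has recommended. A Day 28 PT/INR or aPTT result meeting rule 4, or a late event under rule 5, would pause the study, and on the planned schedule before anyone receives the higher dose. The research monitor also reviews all AEs and can stop the protocol (Appendix A). What has no automatic backstop is a positive DAT alone and late AEs below the stopping-rule thresholds.
- **Always.** The 5 weeks is an estimate, and a late replacement breaks the order.
- **No time saved.** Data cleaning, reporting, the meeting and the sponsor's decision must fit within 20 to 27 days, and no turnaround is stated.

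Two further limits stand. Day 7 CBC and chemistry include hemoglobin and total bilirubin, so hemolysis is not unmonitored at the floor. D-dimer and the Wells scale are not scheduled after 24 hours, so waiting for Day 28 adds no scheduled thrombosis test.

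Moving the cut-off alone would also not clearly put the Day 28 results before the board. The DSMB outputs named in SAP 4.5.3 (Tables 1.1 to 8.3 except 7.4 to 7.6, and Figures 1 and 2) contain no laboratory tables, and the shells for SAP Tables 9 and 10 have no 28-day column. The DSMB charter, which may say more, is not among the documents.

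**Conclusion.** The point holds as a gap between the escalation condition and the data required to judge it. At the permitted minimum the board cannot confirm, for the last subjects infused, that no TEAE occurred over the defined follow-up: 21 of 28 days are unseen, including the only PT/INR, aPTT and DAT measurements after 24 hours.

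On the planned schedule the missing data are collected 20 to 27 days before the next dose could be given. This rests on the Table 6 and Table 8 visit days, recruitment starting only after the last lower-dose infusion, and no late replacement. The time cost of waiting is zero for a turnaround of up to 20 to 27 days and is capped at about 21 days.

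The stopping rules keep the consequence moderate, so the change is worth making but is not a flaw that invalidates the design.

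**What to change.** - In the synopsis, Protocol 6.5 and SAP 1.1, set the minimum for the Cohort 1 and Cohort 2 escalation reviews to data through the 28-day visit for every infused subject. For subjects who leave earlier, require all data to last contact; Protocol 8.4 specifies early-withdrawal laboratory tests only for those who leave before the 7-day visit, so that visit cannot be relied on as a substitute.
- For the final Cohort 3 review, require data through Day 43.
- In SAP 4.5.3, add Day 28 PT/INR, aPTT and DAT results to the DSMB outputs, as a listing or short table, and check the DSMB charter for consistency.
- State the expected turnaround from last required visit to sponsor decision, so that the time cost is known in advance.

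No dose, visit, blood draw or stopping rule changes. The text cost is one sentence in three places plus one added output. The time cost for Cohorts 2 and 3 is none if turnaround is at most 20 to 27 days, and otherwise up to about 21 days. The final Cohort 3 review may move by up to 3 weeks (Day 22 to Day 43), when no subject in this trial is waiting for an infusion.
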